7.6 Secondary Endpoints and Clinical Outcomes

- Mitral regurgitation reduction at 30 days, 6 months, 1 year and annually thereafter over baseline
- All-cause mortality at 30 days, 6 months, 1 year, and annually thereafter
- Recurrent heart failure hospitalization at 30 days, 6 months, 1 year, and annually thereafter
- Re-intervention rates for mitral regurgitation at 30 days, 6 months, 1 year and annually thereafter
- Composite of major adverse events (MAE) defined as cardiovascular mortality, stroke, myocardial infarction, new need for renal replacement therapy, severe bleeding and re-intervention for study device related complications at 6 months, 1 year and annually thereafter
- Change in Left Ventricular End Diastolic Volume (LVEDV) at 6 months and 1 year and annually thereafter over baseline
- Change in Left Ventricular End Systolic Volume (LVESV) at 6 months and 1 year and annually thereafter over baseline
- Change in Pulmonary Artery Systolic Pressure at 6 months and 1 year and annually thereafter over baseline
- Change in 6MWT distance at 6 months and 1 year over baseline

- Change in Quality of Life (QoL) score, as measured by Kansas City Cardiomyopathy Questionnaire (KCCQ), and EQ5D at 30 days, 6 months and 1 year and annually thereafter over baseline
- Change in NYHA Functional Classification at 6 months and 1 year and annually thereafter over baseline
- Change in BNP/NT-pro-BNP level at 6 months and 1 year and annually thereafter over baseline
- Change in tricuspid regurgitation at 6 months and 1 year and annually thereafter over baseline
- Change in effective regurgitant orifice area (EROA) at 30 days, 6 months, 1 year and annually thereafter over baseline
- Change in mitral regurgitant volume at 30 days, 6 months and 1 year and yearly thereafter over baseline

7.7 Patients

7.7.1 Inclusion Criteria

The Investigator has the responsibility of screening potential patients to determine if the patients meet all the inclusion criteria. The following are requirements for entry into the study:

1. Signed and dated ethics committee/institutional review board approved study consent form prior to study related procedures
2. Eighteen (18) years of age or older
3. New York Heart Association (NYHA) Functional Class II, III and ambulatory IV heart failure despite optimal medical therapy
4. Candidate for surgical mitral valve repair or replacement as determined by a Heart Team evaluation
5. For patients whose primary mechanism of mitral regurgitation is functional (secondary; FMR) in nature: Elevated BNP > 150 pg/ml or corrected NT-proBNP of 600 pg/ml measured within 90 days prior to enrollment or heart failure hospitalization within 12 months prior to enrollment. These criteria do not apply to patients whose primary mechanism of mitral regurgitation is degenerative (DMR) in nature.
6. Clinically significant mitral regurgitation (3+ to 4+, as defined in Section 18.0) confirmed by transesophageal echocardiography (TEE) within 90 days prior to intervention, **or** transthoracic echocardiography (TTE) within 60 days prior to intervention
7. Left ventricular ejection fraction (LVEF) \geq 20% determined by TTE within 60 days prior to intervention
8. The primary regurgitant jet is non-commissural. If a secondary jet exists, it must be considered clinically insignificant
9. Patient agrees to return for all required post-procedure follow-up visits
10. For patients whose primary mechanism of mitral regurgitation is functional (secondary; FMR) in nature: Six-minute walk test (6MWT) \geq 150 m and \leq 400 m within 60 days prior to intervention. These criteria do not apply to patients whose primary mechanism of mitral regurgitation is degenerative (DMR) in nature.

7.7.2 Exclusion Criteria

The Investigator at the study site must exclude patients if any of the exclusion criteria are present. The following are the criteria for exclusion from participating in the clinical study:

1. Patient in whom a TEE is contraindicated or screening TEE is unsuccessful

2. Leaflet anatomy which may preclude PASCAL device implantation, proper device positioning on the leaflets, or sufficient reduction in mitral regurgitation that may include:
 - Evidence of moderate to severe calcification in the grasping area.
 - Evidence of severe calcification in the annulus or subvalvular apparatus
 - Evidence of severe Barlow disease
 - Presence of significant cleft or perforation in the grasping area
 - Flail width > 15mm and/or flail gap > 10mm
 - Leaflet mobility length < 8mm
 - Coaptation gap > 5mm
 - Transseptal puncture height < 3.5cm
 - LA diameter ≤ 35mm
 - Presence of two or more significant jets
 - Presence of one significant jet in the commissural area
3. Mitral valve area (MVA) < 4.0 cm² as measured by planimetry (If MVA by planimetry is not measurable, PHT measurement is acceptable)
4. Echocardiographic evidence of intracardiac mass, thrombus, or vegetation
5. Clinical evidence of right sided congestive heart failure and/or echocardiographic evidence of severe right ventricular dysfunction
6. LVEDD > 8.0 cm determined by TTE within 60 days prior to intervention
7. End-stage Heart Failure with inotrope support and/or consideration for LVAD or heart transplant
8. Untreated significant coronary artery disease / stenosis, unstable angina, evidence of acute coronary syndrome, myocardial infarction, transient ischemic attack or stroke within 30 days prior to intervention
9. Clinically significant uncorrected valvular disease or left ventricular outflow obstruction, obstructive cardiomyopathy, poorly controlled rapid atrial fibrillation or flutter, poorly controlled symptomatic brady- or tachy-arrhythmias
10. Any percutaneous cardiovascular intervention, carotid surgery, cardiovascular surgery or atrial fibrillation ablation within 90 days prior to intervention
11. Implant of any rhythm management device (i.e., pacemaker, cardiac resynchronization therapy [CRT] with or without cardioverter-defibrillator [CRT-D]) within 90 days prior to intervention, or revision of any implanted rhythm management device within 90 days prior to intervention

12. Need for emergent or urgent surgery for any reason or any planned cardiac surgery within the next 12 months
13. Any prior mitral valve surgery or transcatheter mitral valve procedure
14. Contraindication to transseptal catheterization
15. Active endocarditis or active infections requiring current antibiotic therapy or last antibiotic treatment was administered within 14 days prior to intervention
16. Active rheumatic heart disease or rheumatic etiology for MR
17. Infiltrative cardiomyopathies (e.g., amyloidosis, hemochromatosis, sarcoidosis), hypertrophic cardiomyopathy, restrictive cardiomyopathy, constrictive pericarditis, or any other structural heart disease causing heart failure other than dilated cardiomyopathy of either ischemic or non-ischemic etiology
18. Tricuspid valve disease requiring surgery or severe tricuspid regurgitation
19. Severe aortic stenosis (aortic valve area $<1.0 \text{ cm}^2$) or severe aortic regurgitation
20. Absence of CRT with Class I indication criteria for biventricular pacing
21. Uncontrolled hypertension (i.e., BP $>180 \text{ mmHg}$ systolic and/or $>105 \text{ mmHg}$ diastolic) or hypotension (i.e., BP $<90 \text{ mmHg}$ systolic)
22. Pulmonary artery systolic hypertension $>70 \text{ mmHg}$
23. Severe symptomatic carotid stenosis ($>50\%$ by ultrasound) or asymptomatic carotid stenosis ($>70\%$ by ultrasound)
24. Severe Kidney Renal Disease with creatinine $>2.5 \text{ mg/dL}$ and/or eGFR $<30 \text{ mL/min/1.73 m}^2$
25. Presence of an occluded or thrombosed IVC filter that would interfere with the delivery catheter, or ipsilateral deep vein thrombosis is present
26. Known hypersensitivity to nitinol or contraindication to procedural medications which cannot be adequately managed medically
27. History of bleeding diathesis or coagulopathy or patient who refuses blood transfusions
28. Pregnant or planning pregnancy within next 12 months. Note: Female patients of childbearing potential need to have a negative pregnancy test performed within 14 days prior to intervention and be adherent to an accepted method of contraception
29. Severe COPD evidenced by oral steroid therapy or oxygen therapy
30. Concurrent medical condition with a life expectancy of less than 12 months in the judgment of the Investigator

31. Patient is currently participating or has participated in another investigational drug or device clinical study where the primary study endpoint was not reached at time of enrollment
32. Patient is under guardianship

7.8 Study Procedures

7.8.1 Pre-screening

Adult patients with clinically significant, symptomatic, mitral regurgitation despite optimal medical therapy and/or are being considered by the heart team for standard mitral valve repair or replacement.

Prior to performing any study specific activities/evaluations, except the standard assessments for this population, the patient must be thoroughly informed about all aspects of the study and the patient must have provided written informed consent.

If local IRB approval is obtained, a screening consent form may be implemented to enable the collection of standard assessments for this population (e.g., TEE and TTE.). Data collected from screening assessments may be used to simultaneously assess the patient's anatomic eligibility for this Study using the PASCAL repair device or other Edwards Clinical Studies using a transcatheter mitral repair or replacement study device. If local IRBs do not allow the use of a screening consent form, all screening assessments will be described under the applicable standard study Informed Consent Form.

7.8.2 Study Informed Consent Process

The patient must sign the Study Informed Consent Form that is currently approved by the institution's overseeing IRB/EC prior to participation. Failure to provide Study informed consent renders the patient ineligible for the study. Study Informed consent must be obtained prior to any study related procedures.

It has to be emphasized that a patient's participation in the trial is voluntary and that the patient may refuse to participate or withdraw from the trial, at any time, without penalty or loss of benefits to which the patient is otherwise entitled.

Signed Screening Consent Form (where applicable) and Study Informed Consent Form must be retained by the Investigational Center for verification during on-site monitoring visits. The

Investigator will retain the original consent forms, a copy will be filed in the sites specific study files, and a copy of the Screening Consent Form (where applicable) and Study Informed Consent Form will be provided to the patient.

The consent forms will be written in the native language/languages of the patient and administered only by the Investigator or authorized designee. The Principal Investigator or delegated person administering the consent must sign and date the Study Informed Consent Form to indicate that the purpose, risks and benefits of the study were explained to the patient and that their signature was witnessed.

The Investigator will retain the original consent form(s), a copy will be filed in the patient's medical record, and a copy of the Screening Consent Form (where applicable) and Study Informed Consent Form will be provided to the patient.

As the Study Sponsor, Edwards Lifesciences must approve any modifications to the Screening Consent (where applicable) and Study Informed Consent Form prior to submission to the ethics committee (EC)/institutional review board (IRB), and/or Competent Authority (as required).

7.8.3 Patient Enrollment

The enrollment overview is shown in Figure 1 in Section 1.2. A patient will be considered a "patient" and "provisionally enrolled" when they have signed the informed consent form. Provisionally enrolled patients will be reviewed by the Heart Team to assure that all inclusion criteria and none of the exclusion criteria are met at which point the patient will be considered "eligible". If a patient has signed the informed consent but are deemed not eligible, the patient is considered a "screen failure" and exit the study.

Eligible patients will be screened for imaging and anatomical suitability and if pre-procedural lab criteria are met. Once these criteria are met, the patient is considered "enrolled".

A Screening/Enrollment Log provided by the Sponsor, will be maintained at the study site. All patients assessed for study participation will be entered on the screening log. "Screen failures" will be recorded on the log with a failure reason.

The screening of patients qualifying for this study should be carried out in a sequential, prospective manner, such that all patients are offered the possibility of participating in the study and are therefore, evaluated according to the selection criteria defined in this protocol.

All patients that have signed the informed consent form, been assessed for study participation and deemed eligible for study participation by meeting the study criteria, will be assigned a

sequential patient ID number by the Study Sponsor. The patient ID number and initials (if applicable) shall be used to identify the patient on the site patient log in order to allow source verification with all study-related documents at the site.

7.8.4 Baseline Evaluation

Baseline evaluation data to be collected will be detailed in the CRF; the data include but is not limited to the information listed in the following table.

Table 3: Baseline Evaluation Data

General Information	Clinical Information	Laboratory Measurements

 • Informed consent • Inclusion/exclusion and other screening evaluation • Demographics 	
 • Medical history (e.g., co-morbidities, EuroSCOREs, STS score, prior cardiovascular interventions / surgeries) • Clinical evaluation (vital signs, height, weight) • NIH Stroke Scale/Modified Rankin Scale* • Concomitant Medication • NYHA classification • TTE and TEE measurements** • 12-lead ECG results • 6MWT results • KCCQ, EQ-5D • MRI results within 60 days of procedure (optional) 	
 • Within 30 days of procedure: Troponin CK-MB • Within 14 days of procedure: CBC and platelets CMP • Within 72 hours of procedure: Serum creatinine • Within 14 days of procedure: βHCG, if applicable • BNP or NT-pro BNP • PTT or PT/INR

*Modified Rankin Scale (mRS) will be conducted at baseline for all patients with a history of stroke and at each follow visit for all patient who had a stroke at any time period during the trial.

**TTE and TEE must be performed within 60 days and 90 days of procedure, respectively

7.8.5 Stroke Assessment and Quality of Life measurements

The following references will be used for stroke assessment and quality of life measurements.

- National Institute of Health (NIH) Stroke Scale Form
http://www.ninds.nih.gov/doctors/NIH_Stroke_Scale.pdf
- Modified Rankin Scale Form

http://www.strokecenter.org/wp-content/uploads/2011/08/modified_rankin.pdf

- EuroQol (EQ – 5D)
<http://www.aaos.org/uploadedFiles/EQ5D3L.pdf>
- Kansas City Cardiomyopathy Questionnaire (KCCQ)
<http://cvoutcomes.org/pages/3214>

7.8.6 Imaging Assessments

Imaging assessments (TTE, TEE) shall be done according to the current version of the core lab echocardiographic acquisition protocol Appendix B. Severity of baseline MR shall be defined as described in Section 18.0 and confirmed by the echo core lab prior to enrollment.

7.8.7 Recommended Antiplatelet / Anticoagulation Therapy

Recommendations for antiplatelet/anticoagulation therapy are detailed in the following sections. Alternative anticoagulation/antiplatelet regimens may be considered according to the needs of individual patients or a hospital's standard practice; these will not constitute a protocol deviation.

7.8.7.1 Pre Procedure Therapy

All patients are recommended to receive aspirin (at least 75-100 mg daily) prior to implant procedure. Patients on warfarin should be asked to discontinue use prior to implant procedure.

7.8.7.2 Procedural Therapy

Heparin will be administered at procedure start. During the procedure, activated clotting time (ACT) will be monitored. It is recommended that Heparin will be administered during the procedure as needed to maintain the patient's ACT at ≥ 250 seconds. The sheaths may be removed when ACT level is appropriate (e.g., reaches < 150 seconds) after implantation of the study devices.

7.8.7.3 Post Procedure Therapy

- Patients without other indication for therapeutic anticoagulation should receive antiplatelet therapy with aspirin (acetylsalicylic acid; ASA) (100 mg daily) for at least 6 months. Additionally patients should receive a combination of Clopidogrel (75mg daily) and ASA (100mg daily) for the first month post-intervention.
- In patients with other indications for therapeutic anticoagulation treatment (e.g. atrial fibrillation), triple therapy is not recommended for the first month post-intervention.

- In addition to the recommended anticoagulation/antiplatelet therapy, periprocedural endocarditis prophylaxis should be administered according to current guidelines⁶.

Table 4: Recommended antiplatelet and anticoagulation therapy

Medication	Pre-Procedure	Intra-Procedure	Post-Procedure	Until 1 Month Follow-Up	Until 6 Month Follow-Up
IV Heparin		X	X		
Aspirin (75-100 mg daily)	X		X	X	X
Clopidogrel (75 mg daily)				X	

7.8.7.4 Device Preparation

A description of device preparation and use is provided in the IFU with the CIB. Investigators must be familiar with the information described in the IFU prior to use of the Edwards PASCAL System. An Edwards Representative that has been trained on the preparation of the Edwards PASCAL System will be in attendance at all implant procedures.

7.8.7.5 Implant Procedure

Refer to the current IFU version for detailed information on the use of the Edwards PASCAL System. Delivery of the implant should be performed under general anesthesia with hemodynamic monitoring in an operating room or hybrid operating room with fluoroscopic and echocardiographic (2D and 3D) imaging capabilities.

The following study procedures will occur during the implant procedure:

- Safety Evaluation
- Transesophageal Echocardiogram
- Angiogram
- ECG
- Invasive Hemodynamic Monitoring, including left side heart pressure measurements and cardiac output pre- and post-implant

⁶ 2014 AHA/ACC Guideline for the Management of Patients with Valvular Heart Disease. J Am Coll Card, Vol 63, No 22, 2014. e57-185.

The date of the implant procedure will be considered as Day 0 for the purpose of determining specified time intervals for the follow up visit.

Procedure data to be collected will be detailed in the CRF; the data include but is not limited to the information listed in the following table.

Table 5: Procedure Information

General Information	Clinical Information	Post-Implant Laboratory Measurements

 • Date of study procedure • Patient identification number • Name of implanting physicians • Access site • Timing of implant procedures • Study device identification & disposition 	
 • Fluoroscopy duration & contrast volume • TEE measurements • Angiographic imaging • Invasive Hemodynamic Monitoring measurements • ECG results • Adverse events • Device malfunction 	
 • Within 12-24 hours post implant: 
 - Troponin - CK-MB - CBC and platelets - Serum creatinine - PTT or PT/INR

7.8.7.6 Post Implant Procedure

The following study procedures will be performed 12-24 hours post implant procedure:

- Clinical Evaluation (includes vital signs, weight and height)
- Safety Evaluation Clinical Laboratory Tests
- Standard 12-lead ECG

7.8.7.7 Discharge

The following study procedures will be performed at discharge or at 7 days of procedure, whichever comes first.

- Clinical Evaluation and Concomitant Medication
- Safety Evaluation
- NIH Stroke Scale
- Clinical Laboratory Tests
- Standard 12-lead ECG
- Comprehensive TTE

Discharge data to be collected will be detailed in the CRF; the data include but is not limited to the information listed in the following table.

Table 6: Discharge Information

General Information	Clinical Information	Laboratory Measurements

 • Discharge date 	
 • Clinical evaluation (vital signs, height, weight) • Concomitant medication (incl. antiplatelet/anticoagulant therapy) • Safety evaluation • NIH Stroke Scale/Modified Rankin Scale* • TTE measurements • 12 lead ECG results 	
 • CK • Troponin, if applicable • CK-MB, if applicable • BNP or NT-pro-BNP • CBC and platelets • Serum creatinine • PTT or PT/INR

7.8.7.8 Follow Up Visits

Follow-up visits will be conducted at 1 month, 6 months, and annually for 5 years post implant.

The following procedures will be conducted during follow up visits:

- Clinical Evaluation (includes vital signs, weight and height), concomitant medication and NYHA classification
- Administration of Health Status Questionnaires at 1 month, 6 months and 1 year
- Administration of 6MWT at 1 month, 6 months and 1 year
- Safety Evaluation
- NIH stroke scale/Modified Rankin Scale*
- Clinical Laboratory Tests (troponin (if applicable), CK-MB (if applicable), BNP or NT-pro-BNP, CBC and platelets, complete metabolic panel, serum creatinine, PTT or PT/INR)
- Standard 12-lead ECG
- Comprehensive TTE
- MRI (optional, as deemed appropriate by Investigator).

Post-procedure follow up visits will be performed on all implanted study patients at 1 month, 6 months, and annually for 5 years post implant procedure intervals as summarized in Table 7.

* Modified Rankin Scale (mRS) will be conducted at baseline for all patients with a history of stroke and at each follow visit for all patient who had a stroke at any time period during the trial. The assessment should be done closest to 90 days post event.

Table 7: Follow-Up Visit Windows

Scheduled Follow-up Interval	Follow-up Window
1 month (30 days)	± 7 days
6 months (180 days)	± 30 days
Annually up to 5 years	± 45 days

During the follow up visits, medical information and assessment results will be entered in the appropriate CRFs.

7.8.7.9 Unscheduled Follow-Up

An unscheduled follow-up is defined as a patient's on-site visit (for medical reasons / adverse event/"symptomatic") at cardiac departments (cardiology, cardiac surgery) of an investigational site or outside hospital. Any unscheduled follow-up shall be documented in the medical file and corresponding CRF pages shall be completed.

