	
Ordinary physical activity results in fatigue, palpitation, dyspnea, or anginal pain.
 
Class III: Patients with cardiac disease resulting in marked limitation of physical activity. They are comfortable at rest. Less than ordinary physical activity causes fatigue, palpitation dyspnea, or anginal pain.
 
Class IV: Patients with cardiac disease resulting in inability to carry on any physical activity without discomfort. Symptoms of cardiac insufficiency or of the anginal syndrome may be present even at rest. If any physical activity is undertaken, discomfort is increased.

Nonstructural Dysfunction	Abnormality extrinsic to the repair device that results in valve dysfunction (stenosis, regurgitation or both)
Patient	A person with the disease (mitral regurgitation) being screened to participate in the clinical study.
Pre-existing condition	A pre-existing condition is one that is present prior to enrollment in the trial
Procedural Success	Device success with evidence of MR reduction \leq MR2+ at discharge and without the need for a surgical or percutaneous intervention prior to hospital discharge. Per patient analysis.
Rehospitalization (M-VARC 2015 Definition and Sponsor)	
Rehospitalization
 
For the purpose of this trial, rehospitalization is defined as any unplanned admission to the hospital (including an emergency department visit) for either a diagnostic or therapeutic purpose following discharge from the index hospitalization. ER (Emergency Room) visits will be explicitly presented separately from the inpatient hospitalizations.
 
Rehospitalizations will be classified as either:
 
 ○ Admission to an inpatient unit (treated by a physician in a hospital for at least a 24 hour period) OR ○ Visit to an ER unit (typically less than 24 hours) AND diagnostic procedure and/or therapeutic intervention 
Additionally, duration of admission will be indicated as lasting:
 
 ○ < 24 hours OR ○ \geq 24 hours 
All rehospitalizations will be classified to determine whether the hospitalization was related to:

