- **CHF (Congestive Heart Failure) hospitalization:** a hospital stay for ≥ 24 hours with signs and/or laboratory evidence of worsening heart AND administration of intravenous or mechanical heart failure therapies. An ER stay for ≥ 24 hours would qualify as a CHF hospitalization endpoint, even absent formal hospital admission, as such a prolonged stay represents a severe episode of heart failure.
- **Other CV hospitalization:** hospitalization due for coronary artery disease, acute myocardial infarction, hypertension, cardiac arrhythmias, cardiomegaly, pericardial effusion, atherosclerosis, stroke, or peripheral vascular disease without qualifying heart failure.
- **Non-CV hospitalization:** hospitalization that is not due to heart failure or other cardiovascular causes, as defined above.

Diagnostic Criteria of Heart Failure

The diagnosis of worsening heart failure is on the basis of:

- 1) Symptoms of worsening heart failure such as increased dyspnea, orthopnea, paroxysmal nocturnal dyspnea, fatigue, decreased exercise tolerance, and/or history of weight gain
- 2) Physical examination evidence of worsening heart failure such as neck vein distention, the presence of a third heart sound, pulmonary rales, ascites or pedal edema, and/or hypotension or signs of worsening end-organ perfusion; and/or
- 3) Diagnostic evidence of worsening heart failure such as radiographic pulmonary congestion, natriuretic peptide levels greater than the upper limit of normal in the absence of conditions known to affect these values (e.g., renal dysfunction, infection), arterial oxygen desaturation or increasing oxygen requirements, and/or acidosis.

No single finding is necessarily diagnostic, and classification should be on the basis of all available clinical evidence.

Examples of intravenous Heart Failure therapies contributing to this definition would include:

- Bolus or continuous infusion of loop diuretic agents
- Continuous infusion of vasodilators such as Nitroglycerin, Nitroprusside, or Nesiritide

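### A heart-failure stay judged unrelated to the device and treated in an emergency room or non-cardiac ward is not reliably required to be recorded, although the endpoint definition can count it

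*Protocol*

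**What the plan says.** **Between-visit recording.** Protocol 7.8.7.9 defines an unscheduled follow-up as an on-site visit for medical reasons "at cardiac departments (cardiology, cardiac surgery) of an investigational site or outside hospital". It then sets the recording duty: "Any unscheduled follow-up shall be documented in the medical file and corresponding CRF pages shall be completed".

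**Endpoint definitions.** In Protocol Section 17, "rehospitalization is defined as any unplanned admission to the hospital (including an emergency department visit) for either a diagnostic or therapeutic purpose" after the index discharge. Each rehospitalization is classed as inpatient or emergency room and as under 24 hours or 24 hours and over, and "ER (Emergency Room) visits will be explicitly presented separately from the inpatient hospitalizations". Heart-failure hospitalization is narrower. It needs a stay of at least 24 hours, worsening heart failure, intravenous or mechanical therapy, and heart failure as the primary problem. On emergency stays, Section 17 says: "An ER stay for ≥ 24 hours would qualify as a CHF hospitalization endpoint, even absent formal hospital admission".

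**Where the data are used.** Protocol 7.6 lists "Recurrent heart failure hospitalization at 30 days, 6 months, 1 year, and annually thereafter" as a secondary endpoint, and SAP 6.4 analyses it by Poisson regression. SAP 7.7 reports the number of subjects with heart-failure rehospitalization. SAP 6.6 makes freedom from rehospitalization for the underlying condition part of 1-year FDA Individual Patient Success.

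**Adverse-event route.** Protocol 8.1 requires every adverse event to be reported from enrollment to the end of participation, each on its own form. Protocol 8.2.1 includes events unrelated to the device, and 8.2.3 makes inpatient hospitalization a criterion for seriousness. Protocol 8.1.2 says pre-existing conditions are not recorded, and calls for an adverse event on worsening when the device, the implant procedure or study procedures caused it.

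**The concern.** The visit definition that triggers CRF pages between scheduled visits is limited by department. The endpoint definition is not. An emergency room or general medical ward is not a cardiac department, and Section 17 itself foresees heart failure presenting alongside pneumonia, renal failure or an exacerbation of COPD, where the patient may well be on another ward. A stay has to be recorded before anyone can decide whether heart failure was primary.

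An unrecorded stay does not show up as a missing value. The SAP's handling of missing data (6.1 and 6.2) does not touch it, and the patient simply counts as event-free. In a single-arm study there is no control arm with the same under-recording to offset the error. Guiding future study designs is a stated objective (Protocol 7.2), so the absolute rate has a use beyond this report.

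**Working it through.** The plan gives no figure to reproduce here, so the check sets the recording rules against the definitions, one kind of stay at a time.

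| Stay after index discharge | Counted under Section 17? | Required by 7.8.7.9? | Required as an adverse event? |
|---|---|---|---|
| Qualifying heart-failure stay in cardiology or cardiac surgery | Yes | Yes | Not needed to close the gap |
| Qualifying heart-failure stay of 24 h or more in an emergency room or non-cardiac ward, due to device or procedure | Yes | No | Yes, under 8.1 and 8.1.2 |
| The same stay, judged due to the underlying disease | Yes | No | Yes on 8.1 and 8.2.1; not on a literal reading of 8.1.2 |
| Emergency visit under 24 h for heart failure, judged unrelated | Not for the heart-failure endpoint; yes for the separate emergency-room presentation | No | Same conflict as the row above |
| New stroke, new dialysis or severe bleed on any ward | Not as heart failure; these are MAE components | Only if seen in a cardiac department | Yes, under 8.1 and 8.2.1 |

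The gap lies in the third row and, for presentation only, the fourth. Three facts make the third row relevant:

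1. Inclusion criterion 3 (Protocol 7.7.1) requires NYHA class II to ambulatory IV heart failure, so 8.1.2 can apply to heart failure in every eligible patient.
2. Protocol 7.8.7.10 mentions seeking hospital records only for patients who cannot be reached for a visit.
3. Scheduled visits are at 1 month, 6 months and 1 year, then yearly to 5 years (Protocol 7.8.7.8). Each includes a safety evaluation, but the protocol does not describe it as a check for every hospital contact. Year-long intervals begin after the 1-year visit.

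**Size.** Neither document gives a heart-failure hospitalization rate or a split by department. If a share m of qualifying stays is recorded by neither route, and follow-up time is unchanged, then

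reported rate = true rate × (1 − m).

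Taking 0.30 stays per patient-year purely as an assumption:

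- m = 0.10: 0.30 × 0.90 = 0.27
- m = 0.20: 0.30 × 0.80 = 0.24
- m = 0.40: 0.30 × 0.60 = 0.18

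These values show the direction and form of the bias. The documents support no particular m, and m = 0 is possible if sites follow 8.1 and disregard 8.1.2.

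For Individual Patient Success, a missed stay changes the result only in a patient who meets all the other components. The error can only raise the proportion, by an unknown amount.

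**The case against.** The strongest reply is that Section 8 already provides a wider route: all adverse events, related or not, in any department, with a reporting deadline. That largely stands. A reader might infer from 7.8.7.9 that everything treated outside cardiology escapes the data, including strokes, dialysis and bleeds. The documents do not support this. Those events fall under 8.1, and 8.1 asks for source documents for events needing CEC adjudication, with safety endpoints as the minimum.

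A second reply is that other passages point towards recording heart failure whatever its cause. Protocol 6.1 lists heart failure and its worsening among the anticipated events, and the causality scale in 8.2.7 has a not-related level that allows for underlying illness. This weakens the literal reading of 8.1.2 but does not remove the text, and sites can reasonably read it differently.

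Three further inferences should be resisted:

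- **That the CRF lacks the fields needed to classify a stay.** The CRFs and the CEC charter are not in the documents, and the short list in 8.1 is the minimum for initial notification only.
- **That any unplanned admission is an endpoint.** All-cause rehospitalization is not listed in 7.6, and emergency visits under 24 hours do not count as heart-failure hospitalizations.
- **That the illustrative rates measure the loss.** They assume a share missed by both routes, which is the point in dispute.

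**Conclusion.** The concern holds in narrowed form. Three rules do not fit together: the department limit in 7.8.7.9, the wider definitions in Section 17, and the relatedness condition in 8.1.2, which also conflicts with 8.1 and 8.2.1. As a result, a heart-failure stay judged unrelated and treated in an emergency room or non-cardiac ward is not reliably required by any route the readable protocol states. This rests on a literal reading of 8.1.2 and on no unseen CRF instruction closing the gap.

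The likely bias is downward for recurrent heart-failure hospitalization and upward for 1-year FDA Individual Patient Success. Its size cannot be estimated from the documents. The primary 30-day MAE composite does not include rehospitalization and is little affected. Severity is minor to moderate: a secondary endpoint and an additional analysis in a descriptive single-arm study, with an inexpensive correction.

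**What to change.** 1. In Protocol 7.8.7.9, replace the cardiac-department limit with any unplanned hospital admission or emergency department visit, in any department of any hospital.
2. Where the CRF does not already do so, have that page record the items Section 17 needs: emergency room or inpatient, under 24 hours or 24 hours and over, the main reason, and any intravenous or mechanical heart-failure therapy given.
3. Reconcile 8.1.2 with 8.1 and 8.2.1 so that heart-failure admissions are recorded whether or not they are judged related to the device or procedures. The first change alone would leave this conflict in place.

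The cost is a sentence in each of two sections, possibly a few CRF fields, and some extra retrieval of records from non-cardiac departments and outside hospitals. Details not collected at the time are hard to reconstruct later.
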